It is proposed to randomly assign at least 100 patients sequentially based on admission; in a single blind, interventional trial, to two separate groups. Patients are going to be selected from our university teaching hospital. patients were randomly assigned to a study group with the use of permuted blocks and stratification using well trusted randomization websites or software programs (SAS). Permuted block randomization list will be transferred from alphabetic symbol by the competent orthopedic supervisor and coded based on the randomization order by manual coding preset by orthopedic supervisor [5]. Double dummy technique may be feasible here as long as we tackled difficulty of providing syringes containing saline. However, the risk of injecting a saline solution subcutaneously (i.e. bleeding complications may develop in persons taking an anticoagulant agent plus unnecessary injections) may outweigh the benefit. Since the investigator do not know which therapy is administrated, the potential for the results to be biased is minimized [6].

The first group is to be on rivaroxaban with dosage according to the orthopedic approved regimen (10 mg once daily 6-10 hours after the surgery; recommended total duration of therapy: 12 to 14 days; ACCP recommendation: Minimum of 10 to 14 days; extended duration of up to 35 days suggested (Guyatt 2012).[3]

The other group will be administered the standard of care (SOC) enoxaparin. Dosage and duration of therapy are illustrated in Table 1 [2].

Drug	Dosage and Duration
Enoxaparin	Once-daily dosing: 40 mg once daily, with initial dose within 9 to 15 hours before surgery, and daily for at least 10 days (or up to 35 days postoperatively) or until risk of DVT has diminished or the patient is adequately anticoagulated on warfarin. The American College of Chest Physicians recommends initiation ≥ 12 hours preoperatively or ≥ 12 hours postoperatively; extended duration of up to 35 days suggested (Guyatt, 2012).

Table 1: *Dosing of SOC drugs used in thromboprophylaxis after orthopedic surgery.*

It is expected here that all medication will be taken for a duration of 10 days after surgery. The type, duration and dose of the thromboprophylactic agents will be discussed with and determined by the competent physician before saying a particular patient can be enrolled.

Study population

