The Patients >18 years who are going to be scheduled to undergo orthopedic surgery in whom decision of thromboprophylaxis taken will be enrolled for inclusion.

Exclusion criteria are based on the approved contraindication listed, for all drugs used, in the drug’s labels and supplemented by data from well trusted compendia like Lexi comp® or Micromedex®. The exclusion criteria are as follows, but not limited to:

- I. Severe hypersensitivity to drugs or any component of the formulation.
- II. Planned intermittent pneumatic compression
- III. A requirement for anticoagulant therapy that could not be stopped
- IV. Severe hypersensitivity reaction (eg, anaphylaxis) to rivaroxaban or enoxaparin.
- V. Received another anticoagulant for more than 24 hours
- VI. Active bleeding or a high risk of bleeding
- VII. Thrombocytopenia associated with a positive test for antiplatelet antibody.
- VIII. Warfarin associated INR more than 1.5 on the day of the surgery
- IX. Conditions preventing bilateral venography
- X. ICU stay after surgery
- XI. Pregnant or breast-feeding

- XII. Creatinine clearance less than 30 ml per minute or acute renal failure before the surgery or at any point during the study period.
- XIII. Moderate or Severe (Child Pugh B or C) hepatic Impairment or in patients with any hepatic disease associated with coagulopathy.
- XIV. Concomitant use of drugs that are both p-glycoprotein inhibitors and moderate to strong cyp3a4 (ketoconazole, itraconazole, lopinavir/ritonavir, ritonavir, indinavir/ritonavir & conivaptan)
- XV. CrCl 15 to 80 mL/min PLUS both P-glycoprotein inhibitors and moderate CYP3A4 inhibitors (eg, abiraterone acetate, diltiazem, dronedarone, erythromycin, verapamil)

The study draft will be submitted to our ethics committee attached to the hospital administration board before enrollment of patients.

Prescribed co-medication of interest.

Because of the well documented effect of drugs affecting CYP3A4 co-prescribed with rivaroxaban, strong inhibitor and inducers listed on <http://medicine.iupui.edu/clinpharm/ddis/clinical-table/> under the guidance of US Food and Drugs Administration(FDA) are contraindicate with rivaroxaban. Patient on these interacting drugs will be excluded.

Outcome measure and follow up.

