The primary efficacy outcomes are the composite of any deep-vein thrombosis, nonfatal pulmonary embolism, or death up to 30 days. The main secondary efficacy outcome is major venous thromboembolism, which is defined as the composite of proximal deep-vein thrombosis, nonfatal pulmonary embolism, or death from venous thromboembolism.

The main safety outcome is the incidence of major bleeding beginning after the first dose of the study drug and up to 2 days after the last dose of the study drug (on-treatment period). Major bleeding is defined as bleeding that is fatal, occurs in a critical organ (e.g., retroperitoneal, intracranial, intraocular, and intraspinal bleeding), or requires reoperation or extra surgical-site bleeding that was clinically overt and is associated with a fall in the hemoglobin level of at least 2 g per deciliter or that requires transfusion of 2 or more units of whole blood or packed cells. Other safety outcomes include any on-treatment bleeding, any on-treatment non- major

bleeding, hemorrhagic wound complications (a composite of excessive wound hematoma and reported surgical-site bleeding), any bleeding that starts after the first oral dose of rivaroxaban and ended up to 2 days after the last dose is administered, adverse events, and death.

Validated clinical prediction rule is recommended to estimate pretest probability of venous thromboembolism. Duplex ultrasonography is the preferred test to diagnose DVT [7]. Many prediction scales are available like *Wells Clinical Models for Evaluating the Pretest Probability of VTE*.

Symptoms and signs of DVT may include unilateral leg swelling, pain in the affected leg, calf tenderness in affected leg, increased leg warmth, erythema of affected leg, or a “palpable cord” may be felt in the affected leg.

Regarding PE, diagnosis is suspected in patients with dyspnea, tachypnea, pleuritic chest pain, cough, and/or fever. Diagnosis begins with initial risk stratification based on presence of shock or persistent hypotension to identify patients at high risk of early mortality.

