For patients with suspected high-risk PE with shock or hypotension, emergency computed tomography(CT) angiography beside transthoracic echocardiography is recommended depending availability and clinical circumstances. While for patients not suspected of having high-risk PE, clinical assessment of likelihood of PE using validated prediction rules and clinical judgement to distinguish between low and high-risk PE may use [8]. However, PE can be diagnosed based on computed tomography pulmonary angiography (CTPA). CT pulmonary angiography is preferred method when available.

It is recommended to have baseline Scr and platelets count. Based on Heparin induced thrombocytopenia, it is advisable to monitor platelets count beginning of the fourth day and every three days until discontinue of Heparins.

Data analysis

The patients in the two groups will be matched in advance for the difference in Patients’ characteristics, VTE risk factors, history of VTE, types of surgery, types of anesthesia and duration of surgery. This ensures fair randomization between groups. Statistical analysis will be performed at an overall significance level of 0.05, adjusted for the primary and secondary end points using non- independent t-test

(SPSS software). Comparisons of the primary end points between treatment groups were performed by means of a log-rank test. To estimate the size of the effect, we will use a Cox regression model. On the other hand, the cost-effective analysis (CEA) will be based mainly on estimating the average cost-effective ratio(ACER) and the incremental cost for each additional cure.

References

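### Exclusion X is not limited to ICU stays planned or known before randomisation, so read literally it can remove randomised patients who had an endpoint event

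*Combined protocol and SAP*

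**What the plan says.** In the Combined protocol and SAP, Study population, exclusion X is the bare phrase "ICU stay after surgery". Two other items in the same list show that the authors could qualify timing. Exclusion II is confined to intended care, "Planned intermittent pneumatic compression". Exclusion XII expressly runs on after entry, covering "acute renal failure before the surgery or at any point during the study period".

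The same section enrols adults "who are going to be scheduled to undergo orthopedic surgery in whom decision of thromboprophylaxis taken will be enrolled for inclusion". Under Study design and randomization, at least 100 patients are assigned to two groups in order of admission. Table 1 gives the main enoxaparin regimen "with initial dose within 9 to 15 hours before surgery", and the same row also cites a postoperative start. Rivaroxaban is given "10 mg once daily 6-10 hours after the surgery".

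Under Outcome measure and follow up, the primary composite is any DVT, non-fatal PE or death within 30 days. Major bleeding is counted from the first dose to 2 days after the last dose. It includes bleeding that is fatal or in a critical organ, and the definition continues "or requires reoperation or extra surgical-site bleeding". The section also sets out a work-up "For patients with suspected high-risk PE with shock or hypotension".

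Data analysis names a log-rank test and a Cox model. Nowhere does the document define an analysis set, or say what happens to a patient who meets an exclusion after randomisation.

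**The concern.** An eligibility criterion should depend only on what is known when the patient is assigned. An unplanned ICU stay after the operation is not known when a patient awaiting surgery is enrolled. Exclusion X can act on such a stay only by removing someone already in the trial.

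The trigger is also not neutral with respect to outcome. PE with shock, bleeding into a critical organ and bleeding that leads to reoperation are all plausible reasons for ICU admission, and all are events that the trial means to count. If such patients are taken out, selection depends on outcome, and the severe end of both the efficacy and the safety results is understated. With about 50 patients per arm, losing one or two events is visible in the reported rates.

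**Working it through.** **1. Can X act after randomisation?** Enrolment is of patients still to be operated on, and assignment follows admission order. The main enoxaparin regimen starts before surgery. Together these make assignment before surgery very likely, though the document does not state the time of randomisation. X itself contains nothing that confines it to what is known at entry.

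**2. Does the trigger overlap the endpoints?** The document describes PE with shock or hypotension, critical-organ bleeding and bleeding that requires reoperation. That these lead to ICU is an inference; the document does not say who is sent there. The link is plausible for PE, some deaths and major bleeding. It is weak for DVT, which is also part of the primary composite.

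**3. Does another rule protect the analysis?** None is stated: there is no intention-to-treat set and no retention rule.

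**4. Size.** The figure of at least 100 is given without event rates, effect size, power or allocation ratio, so it cannot be reproduced. The point does not depend on it. The inputs below are assumptions: 1:1 allocation (50 per arm) and the event rates shown. Simple proportions stand in for the planned time-to-event analysis.

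For *e* events among *n* patients, removing one patient with an event gives (e − 1)/(n − 1). Removing one without an event gives e/(n − 1). With e = 5 and n = 50:

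- starting rate: 5/50 = 10.0%
- one patient with an event removed: 4/49 = 8.2%, a fall of 1.8 points
- two such patients removed: 3/48 = 6.3%
- one patient without an event removed: 5/49 = 10.2%, a rise of 0.2 points

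If a share *f* of events is removed and the true risk is *p*, the observed risk is p(1 − f)/(1 − pf). For example, p = 0.10 and f = 0.25 give 0.075/0.975 = 7.7%.

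| True risk | f = 0 | f = 10% | f = 25% | f = 50% |
|---|---|---|---|---|
| 4% | 4.0% | 3.6% | 3.0% | 2.0% |
| 10% | 10.0% | 9.1% | 7.7% | 5.3% |
| 20% | 20.0% | 18.4% | 15.8% | 11.1% |

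The document gives no value for *f*. For the primary composite the low columns are the more plausible ones, because DVT rarely leads to ICU. For major bleeding the counts may be very small: at an assumed 1 to 2 events in an arm, one removal takes away all or half of them.

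**The case against.** The strongest reply is that X sits in an eligibility list and may simply mean an ICU stay expected beforehand, or direct transfer from theatre. Exclusion XII supports this: where the authors wanted an exclusion to continue through the study they wrote so, and X has no such phrase. No sentence says that a patient who later enters ICU leaves follow-up or analysis. This stands as a reason for caution about intent. It does not close the gap, because exclusion II shows that the authors could also limit a criterion to planned care, and X lacks that limit too. A site applying X literally would be following the protocol.

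Three stronger readings are tempting, and the text does not carry them.

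- A reader might infer that assignment must come before surgery. Table 1 also cites a postoperative start for enoxaparin. Data analysis speaks of matching the groups in advance on duration of surgery, which fits poorly with preoperative assignment. Very likely is as far as the document goes.
- A reader might infer that severe events will drop out. The ICU link is inferred and its frequency unknown, so the supportable statement is that they can.
- A reader might infer that X acts unequally by arm, because enoxaparin may be given before surgery and rivaroxaban after it. X does not depend on whether a dose was given; read literally, it removes an early ICU patient in either arm. A bleed before the first rivaroxaban dose is already outside the on-treatment window, so X deletes no main-safety event there. Any imbalance in that interval comes from when the safety window opens, which is a separate matter. A biased risk ratio could be computed only by assuming unequal removal shares, for which the document gives no basis.

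**Conclusion.** The concern holds in a limited form. As worded, X permits removal of a randomised patient for a post-randomisation event that overlaps the PE, death and major-bleeding outcomes, and nothing in the analysis plan prevents it. With an assumed 50 patients and 5 events per arm, each removed patient with an event costs that arm about 2 percentage points; a removed patient without one shifts it by about 0.2. The total effect depends on the unknown share of events leading to ICU. It may be small for the primary composite, and is potentially larger in relative terms for major bleeding. The conclusion rests on assignment before surgery, which is likely but not stated, and on the inferred path from severe events to ICU. No direction of bias between the arms is claimed. Severity: should-fix, with moderate confidence.

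**What to change.** Limit exclusion X to an ICU stay planned or known at the time of randomisation. Add a retention rule: any randomised patient with a later ICU stay remains in follow-up to day 30 and is analysed in the assigned group. This applies to the primary outcome, and to major bleeding within the existing on-treatment window (first dose to 2 days after the last dose). Let the same sentence cover the part of exclusion XII that applies after entry, since the gap there is the same. The rule concerns follow-up and analysis only; treatment decisions for these patients are not addressed here.

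The cost is one reworded criterion and one added sentence. A few sicker patients stay in follow-up, and reported event rates may be slightly higher. The change needs to be in place before patients are enrolled, because outcomes lost when follow-up stops may not be recoverable at analysis.

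### Exclusion criteria X and XII can be met after allocation and no analysis population is named, so applied literally they would remove randomised patients

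*Combined protocol and SAP*

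**What the plan says.** The Study population section opens its exclusion list by stating that "Exclusion criteria are based on the approved contraindication listed, for all drugs used", with the drug labels as the source. Item XII is "Creatinine clearance less than 30 ml per minute or acute renal failure before the surgery or at any point during the study period". Item X is "ICU stay after surgery".

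Study design and randomization proposes to "randomly assign at least 100 patients sequentially based on admission". Table 1 has enoxaparin starting 9 to 15 hours before surgery, and also cites a guideline option of starting at least 12 hours before or after it. Rivaroxaban starts 6 to 10 hours after surgery. About 10 days of treatment are expected.

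Under Outcome measure and follow up, the primary composite is "any deep-vein thrombosis, nonfatal pulmonary embolism, or death up to 30 days". Major bleeding, the main safety outcome, is counted from the first dose until 2 days after the last. That section recommends a baseline serum creatinine and schedules no repeat. The only scheduled later blood test is the platelet count tied to heparin.

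Data analysis says "Comparisons of the primary end points between treatment groups were performed by means of a log-rank test" and "To estimate the size of the effect, we will use a Cox regression model". It names no intention-to-treat, per-protocol or safety population. It does not say what happens to a patient who meets an exclusion criterion after allocation.

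**The concern.** An exclusion criterion should use only what is known before allocation. Acute renal failure can follow major bleeding or a severe embolism, and an ICU stay can follow either. Removing a randomised patient for one of these events makes membership of the analysed group depend on what happened after treatment was assigned, and possibly on the outcome itself. The arms are then no longer guaranteed to be comparable.

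The wording also leaves a choice to be made once data are in hand: the patient could be taken off drug only, censored at the event, or deleted. These options treat events differently, and the plan does not choose between them.

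**Working it through.** **Timing.** XII runs through the study period, and primary outcomes are counted to day 30, so its window extends past allocation whenever allocation takes place. X can be judged only after surgery. Patients are assigned in order of admission, and the preoperative enoxaparin regimen requires allocation before surgery. X can therefore also be met after allocation.

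**What each reading does.**

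| Reading of XII | Primary composite to day 30 | Major bleeding, on-treatment |
|---|---|---|
| Stop drug, keep following | Unaffected | Window ends 2 days after the early last dose, instead of about day 10 + 2 = 12 |
| Censor at renal failure | Earlier events count, later ones are lost | Later events are lost |
| Delete the patient | Earlier and later events are lost | Earlier and later events are lost |

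**Size under deletion.** The plan has no figure of its own to reproduce here: the 100 patients come without power, event rate or effect size, and the total is not in dispute. Assumptions, none from the documents: 50 per arm (no allocation ratio is stated), a true risk ratio of 1.00, event risk p, and a fraction f of event patients deleted in one arm only.

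- Observed risk in the affected arm = p(1 − f)/(1 − pf).
- Expected deletions in that arm = 50pf.
- Chance of at least one deletion (Poisson) = 1 − exp(−50pf).
- Ratio = unaffected arm over affected arm. The inverse applies if the other arm is affected.

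| Outcome | p | f | Observed risk | Ratio (inverse) | Expected deletions | Chance of at least one |
|---|---|---|---|---|---|---|
| Primary | 0.10 | 0.02 | 0.0982 | 1.018 (0.982) | 0.10 | 10% |
| Primary | 0.10 | 0.05 | 0.0955 | 1.047 (0.955) | 0.25 | 22% |
| Primary | 0.05 | 0.02 | 0.0490 | 1.019 (0.981) | 0.05 | 5% |
| Primary | 0.05 | 0.05 | 0.0476 | 1.050 (0.952) | 0.125 | 12% |
| Major bleeding | 0.04 | 0.02 | 0.0392 | 1.020 (0.980) | 0.04 | 4% |
| Major bleeding | 0.04 | 0.05 | 0.0381 | 1.051 (0.952) | 0.10 | 10% |

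At a common p, equal deletion in both arms leaves the ratio at 1.00.

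**Sensitivity to one deleted event patient** (log-method 95% CI):

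- Primary at 10%, no deletion: (5/50)/(5/50) = 1.00 (0.31 to 3.24).
- Primary at 10%, one deletion: (5/50)/(4/49) = 1.23 (0.35 to 4.29). In the other direction, 0.82.
- Major bleeding at 4%, one deletion: (2/50)/(1/49) = 1.96 (0.18 to 20.9). In the other direction, 0.51.

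These show how fragile sparse counts are. They are not expected bias: each needs a whole event patient to be deleted, and the last column of the table gives the chance of that.

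**Power is not the issue.** For assumed risks of 20% and 10% at two-sided 0.05, power is 28.6% with 50 per arm and 27.6% with 48.

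**The case against.** The strongest reply is that the list is drawn from label contraindications, so XII may be no more than a limit on giving drug. Nothing in the text says that a patient who meets it later is censored or deleted. This stands: the stop-drug reading is open. It does not settle the matter, because the item is written as an exclusion, no discontinuation rule appears, and no analysis population is named. Nor is that reading harmless throughout. It leaves the 30-day composite alone, but it shortens the on-treatment window for major bleeding.

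A second reply is that the trigger would seldom be seen, since only baseline creatinine is planned. This also stands, and it lowers the likely count. It has another side: later renal failure would be found ad hoc, probably in sicker patients, and detection could differ by arm.

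A third is that every rate is assumed and random error is far larger than the bias. That is correct, and it limits the point to a minor one.

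A reader might infer that the plan commits the sponsor to dropping these patients, or that the comparison is tilted toward one drug. The documents support neither. They leave the handling open and give no basis for a direction.

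**Conclusion.** The point holds as a minor one. Criteria X and XII reach past allocation, and the plan does not protect the randomised comparison against applying them literally. With 50 per arm, assumed event risks of 4% to 10%, and deletion of 2% to 5% of event patients in one arm only, the expected ratio moves from 1.00 to about 1.02 to 1.05, or 0.98 to 0.95 in the other direction. If XII means only stopping drug, the primary composite is not biased by removal, and what remains is the shortened bleeding window.

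The number of patients affected cannot be derived, because the documents give no rate for renal failure or ICU admission. The ratios of 1.23 and 1.96 might be read as the bias to expect. They are not: they describe a single unlucky deletion, and their intervals are too wide to carry information. The case for acting is that the ambiguity can be foreseen and costs almost nothing to remove.

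**What to change.** - Limit XII to creatinine clearance <30 ml/min or acute renal failure before randomisation.
- Limit X to an ICU stay that is already planned at randomisation.
- State that creatinine clearance <30 ml/min or acute renal failure after randomisation is a reason to stop study drug, or not to start it if no dose has been given, and not a reason to leave the study. Requiring a stop, rather than a review, keeps the rule as strict as the contraindication behind it.
- State that every randomised patient is followed to day 30 and that the primary composite is analysed in the assigned arm.
- Keep major bleeding on-treatment as defined, and also report it to day 30 by assigned arm.

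The cost is two edited criteria, a few sentences, and recording of bleeding to day 30, a point to which the primary outcome is already followed. The downside is that patients who stop treatment stay in the analysis and slightly dilute the contrast between the drugs.

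### Major bleeding is counted from each patient's own first dose, but the stated first-dose times differ by arm, so the main safety comparison has no common start

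*Combined protocol and SAP*

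**What the plan says.** The section on outcome measures and follow-up defines the main safety outcome as "major bleeding beginning after the first dose of the study drug and up to 2 days after the last dose" of study drug. Any on-treatment bleeding and on-treatment non-major bleeding are further outcomes under the same label. Another bleeding outcome begins at the first oral rivaroxaban dose. Hemorrhagic wound complications, adverse events and death are listed without a dose-anchored window.

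The section on study design and randomization gives rivaroxaban as "10 mg once daily 6-10 hours after the surgery". Table 1 gives enoxaparin "with initial dose within 9 to 15 hours before surgery", and the same cell cites guideline advice of "initiation ≥ 12 hours preoperatively or ≥ 12 hours postoperatively". A double dummy is discussed there, with a warning that the risk of saline injections may outweigh the benefit; it is not adopted.

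Stated durations also vary. Table 1 has enoxaparin "daily for at least 10 days (or up to 35 days postoperatively". The rivaroxaban text recommends 12 to 14 days and adds "ACCP recommendation: Minimum of 10 to 14 days; extended duration of up to 35 days suggested". The section then says: "It is expected here that all medication will be taken for a duration of 10 days after surgery".

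**The concern.** When counting begins at the first dose and the first dose comes at a different time in each arm, the counting rule depends on the arm. Under the Table 1 preoperative start, the same qualifying bleed three hours after surgery counts for an enoxaparin patient and not for a rivaroxaban patient. A rivaroxaban patient who bleeds before the first dose and is never dosed has no window at all. Randomisation cannot balance this, and the relative bias does not shrink with more patients.

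Part of any observed safety difference would then come from the definition and not from the drugs. The trial's aim includes a safety evaluation, and its introduction complains that bleeding data are hard to compare across trials because definitions are not standardised.

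**Working it through.** The plan gives no figure to reproduce here, so the check is arithmetic on the stated times.

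**Inputs.** Hour 0 is the end of surgery, and operating time is ignored unless stated. Rivaroxaban starts at +6 to +10 h. Enoxaparin starts at −15 to −9 h (Table 1), or by the guideline at −12 h or earlier, or at +12 h or later. Both windows are assumed to end at day 12 (10 days plus 2), which is 288 h.

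**Start gap = rivaroxaban start − enoxaparin start.**
- Table 1 preoperative start: 6 + 9 = 15 h to 10 + 15 = 25 h. Enoxaparin opens earlier, with operating time to be added.
- Guideline start exactly 12 h before: 6 + 12 = 18 h to 10 + 12 = 22 h earlier.
- Guideline start exactly 12 h after: 12 − 10 = 2 h to 12 − 6 = 6 h later. A later start widens this, and no upper limit is stated.

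No option gives a gap of zero.

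**Ratio with no true difference.** If bleeding is spread evenly over the hours at risk (an assumption), the rivaroxaban/enoxaparin ratio is the ratio of hours counted. Rivaroxaban counts 288 − 6 = 282 h to 288 − 10 = 278 h.

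| Enoxaparin start | Calculation | Ratio |
|---|---|---|
| Preoperative, hours before surgery carry no risk | 282/288; 278/288 | 0.98; 0.97 |
| 9 to 15 h before, full risk before surgery | 282/297; 278/303 | 0.95; 0.92 |
| 12 h before, full risk before surgery | 282/300; 278/300 | 0.94; 0.93 |
| 12 h after | 278/276; 282/276 | 1.01; 1.02 |
| 24 h after (illustrative) | 278/264; 282/264 | 1.05; 1.07 |

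**Sensitivity of the 9-to-15-hour, full-risk row.**
- An assumed operating time of 1 to 3 h gives 282/298 = 0.95 to 278/306 = 0.91.
- An end at day 16 (14 + 2; 384 h) gives 378/393 = 0.96 to 374/399 = 0.94.
- An end at day 37 (35 + 2; 888 h) gives 882/897 = 0.98 to 878/903 = 0.97.

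**In events.** The plan says "It is proposed to randomly assign at least 100 patients sequentially based on admission". With 50 per arm (1:1 assumed) and an assumed major-bleeding risk of 1 to 4%, each arm expects 50 × 0.01 = 0.5 to 50 × 0.04 = 2 events. The preoperative-start shift is the expected count times the share of the enoxaparin window that lies outside the rivaroxaban window:
- No risk before surgery: 0.5 × 6/288 = 0.01 to 2 × 10/288 = 0.07.
- Full risk before surgery: 0.5 × 15/297 = 0.03 to 2 × 25/303 = 0.17.

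Clustering of bleeds around surgery would move the preoperative-start ratio further from 1. The documents give no timing from which to size this.

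**The case against.** The strongest reply is that the effect is small and partly contained by the plan's own definition. The major-bleeding definition appears to tie the haemoglobin-fall and transfusion criteria to bleeding outside the surgical site. On that reading, blood lost at the operative site qualifies only if it is fatal, in a critical organ or requires reoperation. Most operative blood loss would then be uncounted in both arms. This stands, and it limits how far clustering around surgery could move the main outcome. It does not help any on-treatment bleeding or on-treatment non-major bleeding, where no such restriction is stated and the asymmetry is likely to matter more.

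It is also fair that giving the 9 to 15 preoperative hours full risk inflates the ratio. The patient has not yet been operated on, and active bleeding or high bleeding risk is an exclusion. The no-risk row belongs in the range for that reason.

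On-treatment windows are legitimate as supportive analyses, and the outcomes without a dose-anchored window may pick up early bleeds in both arms. Neither point corrects the main safety outcome. The outcome tied to the first oral rivaroxaban dose does not help either, because enoxaparin patients take no such dose.

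A reader might infer that the plan is built to favour rivaroxaban, or that the safety ratio could be halved by the counting rule alone. The documents support neither reading. The direction depends on which enoxaparin start is used, and a large distortion needs a share of bleeding before the first rivaroxaban dose that nothing in the documents supplies.

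**Conclusion.** The defect holds: followed as written, the plan counts major bleeding over windows that begin at different times in the two arms, and the Data analysis section names no analysis that aligns them. Confidence is high on the missing common start and lower on its impact.

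With a preoperative enoxaparin start, the bleeds counted in that arm only are those during the operation and the first 6 to 10 hours after it that are fatal, in a critical organ, require reoperation, or are overt, outside the surgical site and meet the haemoglobin or transfusion criterion. On even spread to day 12 the distortion is 2 to 8% towards rivaroxaban (ratio 0.98 down to 0.92), or 1 to 2% the other way with a 12-hour postoperative start. At about 100 patients this is a fraction of an event, so it would seldom be visible in the result. These sizes rest on assumed even spread, equal window ends, 1:1 allocation and a 1 to 4% risk. It should be fixed because the correction is cheap and the direction is not set in advance.

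**What to change.** Make the main safety comparison major bleeding by randomised arm, over one window with the same start and end in both arms.

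- **Start:** randomisation, with a statement that it precedes any study dose. Patients are assigned on admission and enrolled with surgery still ahead, so this looks feasible, though the plan does not say so.
- **End:** one fixed postoperative day that matches the reconciled treatment duration, for example day 12 (the plan's 10 days plus 2).
- **Analysis set:** state that patients who meet exclusion X (ICU stay after surgery) or XII (acute renal failure during the study) after randomisation stay in this comparison. Both can arise only after assignment, and dropping those patients would undo it. This concerns the analysis, not treatment.
- **Supportive analysis:** keep first dose to last dose plus 2 days.
- **Other outcomes:** redefine the outcome tied to the first oral rivaroxaban dose so that one window serves both arms. The on-treatment bleeding outcomes need the same common-window version.
- **Reconciliation:** the conflicting first-dose timing and duration statements in the design section and Table 1 must be reconciled. No view is taken on which is right.

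The cost is rewording, plus recording the date and hour of bleeding onset from randomisation in both arms. Efficacy follow-up already runs to 30 days, so an end at day 12 or 16 adds no follow-up; an end at day 37 would. Counting bleeds before the first rivaroxaban dose slightly dilutes any true drug difference, which is the reason to keep the on-treatment analysis beside it.
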